5.2.4. Evaluable Population

The evaluable population includes all ITT subjects who have at least one post-baseline efficacy assessment performed, experienced no major protocol deviations during the study, and have received a minimum of one cycle of treatment are considered to be in the evaluable population.

5.2.5. PK Population

The PK Population includes all subjects who receive at least one dose of study treatment and have at least one measureable plasma/serum exposure. If any subjects are found to be noncompliant with respect to dosing, have incomplete data, or encounter other circumstances that would affect the evaluation of the PK, a decision will be made on a case-by-case basis as to the inclusion of his PK data in the statistical analysis.

5.2.6. Immunogenicity Population

The immunogenicity Population includes all subjects who receive at least one dose of durvalumab and have at least one measureable PK and/or ADA concentration. If any subjects are found to be noncompliant with respect to dosing, have incomplete data, or encounter other circumstances that would affect the evaluation of the PK and/or ADA, a decision will be made on a case-by-case basis as to the inclusion in the analysis.

CELGENE PROPRIETARY INFORMATION

6. SUBJECT DISPOSITION

Subject disposition (analysis population allocation, entered, discontinued, along with primary reason for discontinuation from study as stated in the study CRF) will be summarized using frequency and percentage for both cohort and follow-up phases.

This will be provided for both ITT and Safety populations. A summary of subjects enrolled by site will be provided. Protocol deviations will be summarized using frequency tabulations. The details will be provided in the study Tables and Listings.

7. DEMOGRAPHICS AND BASELINE CHARACTERISTICS

Data on the demographics and baseline clinical characteristics will be summarized for the Safety population, as well as the ITT. Summary for mITT population will be presented only if there is a substantial difference between ITT and mITT populations.

7.1. Demographics

Demographic characteristics consist of age, gender, race, ethnicity, etc., will be summarized for the ITT population and safety population. Age is defined as the integer part of $(\text{informed consent date} - \text{birth date} + 1)/365.25$.

7.2. Baseline Clinical Characteristics

Baseline values are defined as the last assessment of a particular parameter (e.g., vital signs, weight, or laboratory assessments) prior to administration of the first dose of IP in the treatment phase of the study, unless noted otherwise for a particular assessment. In most cases, baseline assessments are those performed before dosing on Day 1 of Cycle 1. When there are retested values, the retest values will be used for the analysis.

Data collected in the CRF, including medical history, prior treatments, disease diagnosis, etc., will be summarized using frequency tabulations by system organ class and preferred term.

A similar summary will be generated for the currently active abnormalities only, per body system. Individual subject listings will be provided to support the tables.

The following baseline of clinical characteristics will also be summarized:

- The WHO classification, IPSS classification, and FAB classification of MDS.
- The Eastern Cooperative Oncology Group (ECOG) performance status, and time since initial diagnosis of MDS, which is defined as the number of months from the date of initial diagnosis to the date of informed consent.
- The MDS diagnosis classification at study entry by WHO, IPSS, and FAB criteria, and ECOG performance status, will be summarized categorically. Time since initial diagnosis will be summarized descriptively.

7.3. Medical History

- Medical history data, including any prior or concomitant diseases and the status of diagnosis if available, will be summarized using frequency tabulations by system organ class and preferred term according to (MedDRA) version 19, or higher.

7.4. Prior MDS Treatment

- A frequency table by Anatomical Therapeutic Chemical (ATC) class and preferred name will be provided according to the coding scheme of the latest version of WHO drug dictionary for all prior treatments of MDS recorded on the CRF, which includes all medications taken for any indication within the 4 weeks (28 days) prior to the first dose of IP. The start date and end date of the treatment if available, the dose and frequency will also be summarized.

7.5. RBC and Platelet Transfusion History

- Documentation of all red blood cell and platelet transfusions received by the subject within 8 weeks (56 days) prior to the first dose of IP will be reported in a listing if recorded on the appropriate CRF. The transfusion data may include the type of transfusion, number of units, reason for, and date of transfusion.

7.6. Pregnancy

- A by-subject listing of status of childbearing potential, pregnancy tests and results as well as menstrual cycles regularity, will be provided for all female patients of childbearing potential if recorded in CRF. For female patients without childbearing potential, the status of hysterectomy, the status of bilateral oophorectomy, and the status of consecutive naturally post-menopausal will also be reported.

8. STUDY TREATMENTS AND EXTENT OF EXPOSURE

Following variables regarding the extent of study drug exposure are defined and will be summarized.

- ***Treatment Duration:***
 - Definition: (study treatment end date – first study drug start date + 1)/30.4167.
 - Descriptive summary statistics will be provided. An additional table will be created for all treated subjects, displaying number of subjects by cycle. A by-subject listing of all exposure information collected on the CRF will be provided.
- ***Number of Treatment Cycles:***
 - Descriptive summary statistics will be provided for safety population.
- ***Duration of exposure:***
 - Definition: total number of days on the study drug during the treatment period (excluding the periods of dose break per protocol or dose interruptions).
 - Descriptive summary statistics will be provided for safety population.
- ***Average Length of Cycle:***
 - Definition: the number of days on treatment divided by the number of cycles.
 - Descriptive summary statistics will be provided for safety population.
- ***Average Number of Days Dosed Per Cycle:***
 - Definition: the number of days a subject is dosed divided by the number of cycles the subject had.
 - Descriptive summary statistics will be provided for safety population.
- ***Cumulative Dose:***
 - Definition: the sum of all doses taken during the treatment period (in milligrams).
 - Descriptive summary statistics will be provided for safety population by cohort and overall.
- ***Average Daily Dose:***
 - Definition: the cumulative dose of the study drug divided by the number of days dosed (received a non-zero dose).
 - Descriptive summary statistics will be provided for safety population.
- ***Dose Intensity:***

- Definition: the cumulative dose of the study drug divided by treatment duration of the study drug.
- Descriptive summary statistics will be provided for safety population.
- ***Dose Modification:***
 - Descriptive summary statistics will be provided for safety population, including
 - subjects who have at least one dose reduction/interruption,
 - time to first dose reduction/interruption,
 - first dose reduction/interruption due to AE,
 - duration of first dose reduction/interruption due to AE.

9. PRIOR/CONCOMITANT MEDICATIONS AND PROCEDURES

Prior medications are defined as medications that were started before the date of first dose of IP (whether or not ended before the date of first dose). Prior medications that continue into study treatment period will be also reported as concomitant medication. Prior medications will be coded in the latest version of the WHO drug dictionary. Medication not in the WHO drug dictionary will be classified as “Not Coded” in the analysis. A frequency table by Anatomical Therapeutic Chemical (ATC) class and preferred term will be provided. A listing of prior medications documented on the CRF will also be provided. All prior and concomitant medications (prescription and non-prescription), treatments, and therapies taken from 84 days (12 weeks) prior to the first dose of IP, up to 28 days after the last dose of IP or up to the last study visit, whichever date is later, will be analyzed. All prior treatments for MDS, including ESAs, thrombopoiesis-stimulating agents (TSAs), iron-chelating agents, chemotherapy, cytotoxic therapy, investigational agents, or other medications considered supportive care for MDS should be recorded on the respective CRF(s) regardless of discontinuation date of treatment.

Concomitant medication is defined as all medications taken from the date of first dose until 28 days after the last dose of IP or until the last study visit, whichever period is longer. Concomitant medications will be coded in the latest version of the WHO drug dictionary. Medication not in the WHO drug dictionary will be classified as “Not Coded” in the analysis. The Anatomical Therapeutic Chemical (ATC) coding scheme of the WHO will be used to group medications into relevant categories. A frequency table by ATC class and preferred term will be provided. All concomitant medications documented on the CRF will be listed for the safety population.

The total number of prior and concomitant medications and the number and percentages of patients with at least one prior and one concomitant medication will be summarized. The number and percentages of all prior and concomitant medications will be summarized and listed by drug class and preferred term.

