6.1.4. Prior Medications and MDS Treatments

All prior and current medications, including, prescription, over-the-counter, and herbal preparations taken for any indication within the 4 weeks (28 days) prior to the first dose of IP will be recorded on the appropriate CRF.

All prior treatments for MDS will be recorded on the respective CRF(s) regardless of dates of treatment.

Documentation of the subject's prior treatment with an adequate course of injectable HMA (see inclusion criterion number 3) should be sent to the sponsor at least 48 hours ahead of the planned date of first dose to allow time for sponsor review prior to initiating IP. Failure to clearly establish refractory disease (no objective response of HI or better) during or following an adequate course of injectable HMA will preclude the subject from being enrolled into the study.

Per inclusion criterion number 5, the last dose of injectable HMA must have been within 16 weeks prior to the subject's informed consent signature date in order to be considered for this study. Also, there may not be less than 3 weeks between the subject's last dose of injectable HMA and the planned first dose of IP in this study (inclusion criterion number 6).

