6.7.9. Concomitant Medications/Significant Non-drug Therapies/Concomitant Procedures

All prescription, over-the-counter, or herbal medications and therapeutic procedures received within 4 weeks (28 days) prior to the first dose of IP, until 28 days after the last dose of CC-486 and 90 days after durvalumab (or until the treatment discontinuation visit, whichever period is longer) must be recorded on the appropriate CRF page. Concomitant medications, therapies, and procedures are those that are received by the subject during their participation in the treatment phase of the study. If a medication, therapy, or procedure ended or was stopped prior to the first dose of IP, it will be recorded as a prior medication or as a part of the subject's medical history, as appropriate. See Section 9 for details regarding concomitant medications and procedures.

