9. CONCOMITANT MEDICATIONS AND PROCEDURES

All prior and concomitant medications (prescription and non-prescription), treatments, and therapies taken from 28 days (4 weeks) prior to the first dose of IP, up to 28 days after the last dose of CC-486 (90 days for durvalumab), or up to the last study visit, whichever date is later, must be recorded on the appropriate CRF.

All prior treatments for MDS, including ESAs, thrombopoiesis-stimulating agents (TSAs), iron-chelating agents, chemotherapy, cytotoxic therapy, investigational agents, or other medications considered supportive care for MDS should be recorded on the respective CRF(s) regardless of discontinuation date of treatment.

Concomitant medications should be kept to a minimum during the study. However, if considered necessary for the subject's welfare and are unlikely to interfere with the IP, they may be given at the discretion of the investigator.

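### SAP 7.4 and SAP 9 set medication rules that match neither the protocol's collection rules nor the SAP's own adverse-event window; only descriptive tables are affected

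*SAP*

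**What the plan says.** **SAP 9 (Prior/Concomitant Medications and Procedures)** has two window sentences. The first gives the analysis window for prior and concomitant medications as "taken from 84 days (12 weeks) prior to the first dose of IP, up to 28 days after the last dose of IP"; a later final visit extends it. The second defines concomitant medication by the span "from the date of first dose until 28 days after the last dose of IP or until the last study visit"; the longer of the two applies. Neither sentence separates durvalumab from CC-486.

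**Protocol Section 9** has a shorter look-back: it covers medications "taken from 28 days (4 weeks) prior to the first dose of IP". Its end point differs by product: 28 days for CC-486 and 90 days for durvalumab, extended by any later visit. Protocol 6.7.9 uses the same two periods, with recording "until 28 days after the last dose of CC-486 and 90 days after durvalumab".

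**SAP 7.4 (Prior MDS Treatment)** specifies a frequency table whose content is "all prior treatments of MDS recorded on the CRF, which includes all medications taken for any indication within the 4 weeks (28 days". Those 28 days run back from first dosing. Protocol 6.1.4 describes two collections. One holds medications for any indication over 28 days. The other holds MDS therapy, under this rule: "All prior treatments for MDS will be recorded on the respective CRF(s) regardless of dates of treatment".

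**The concern.** The Prior MDS Treatment table describes the population on which the trial is built, namely subjects whose disease did not respond to an injectable hypomethylating agent or who could not tolerate one. If SAP 7.4 is programmed as written, an antibiotic or antiemetic taken in the four weeks before first dose is counted as prior MDS treatment.

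The tail in SAP 9 matters because SAP 11.1 counts adverse events as treatment-emergent up to 90 days after durvalumab. An immune-mediated event starting on, say, Day 60 after the last infusion enters the adverse-event tables. A steroid first given for it that day can fall outside the concomitant-medication table. An event and its treatment should share one window.

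The 84-day look-back tells a reader that the report covers 12 weeks of prior medication, when the protocol asks sites for only 4 weeks of non-MDS medication.

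**Working it through.** There is no planned figure to reproduce, so the check sets the rules side by side and counts days.

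| Item | Protocol | SAP |
|---|---|---|
| Look-back, non-MDS medications | 28 days (Section 9, 6.1.4, 6.7.9, Table 2 footnote h) | 84 days in SAP 9; 28 days in SAP 7.4 |
| End after CC-486 | 28 days, or last visit if later (Section 9, Table 2) | 28 days after last IP, or last visit if later |
| End after durvalumab | 90 days, or last visit if later (Section 9, Table 2; 90 days also in 4.1.5.2 and 6.7.9) | 28 days after last IP, or last visit if later (SAP 9); 90 days for treatment-emergent events (SAP 11.1) |
| Prior MDS treatments | Recorded separately, no date limit (6.1.4, Section 9, Table 2 footnote g) | SAP 7.4 adds any-indication medications of the last 28 days; SAP 9 repeats that there is no date limit |

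**Look-back.** Each document's week and day figures agree: 12 × 7 = 84 and 4 × 7 = 28. The excess is 84 − 28 = 56 days. A non-MDS drug stopped between Day −84 and Day −29 is not collected, so the SAP window is wider than the data. A wider analysis window excludes nothing that was recorded.

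**Tail after durvalumab.** The gap depends on which product was taken last, because SAP 9 counts from the last dose of any IP.

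- Durvalumab was the last IP dose: 90 − 28 = 62 days outside the SAP window.
- The last cycle's 21-day CC-486 course was completed: durvalumab is given on Day 1 and the last CC-486 dose on Day 21, which is 20 days later. The SAP window ends 20 + 28 = 48 days after durvalumab, and the gap is 90 − 48 = 42 days.
- CC-486 continued alone after durvalumab stopped (allowed by Protocol 4.1.3): the gap shrinks day for day and is zero once the last CC-486 dose is 62 or more days after the last durvalumab dose.
- A later study visit took place: the window extends to that visit. Protocol 4.1.5.2 schedules a visit 90 (±3) days after the last durvalumab dose, which closes the gap to within the visit allowance.

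**Subjects who could be affected.** The protocol gives 65 enrolled in total. The Amendment 4 justification gives 13 in the monotherapy run-in and says that both Phase 2 monotherapy cohorts filled Stage 1. Assuming 16 in each of those cohorts, 65 − 13 − (2 × 16) = 20 is a ceiling on combination subjects.

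**SAP 7.4.** Two readings of the inclusion clause are open, and neither gives the intended table.

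- As an inclusion, it adds non-MDS drugs.
- As a 28-day limit on MDS treatments, it removes most of the qualifying therapy. Inclusion criteria 5 and 6 put the last injectable dose at least 3 weeks (21 days) before first IP dose and allow it up to 16 weeks before consent. Only a last dose 21 to 28 days before first IP dose would then fall inside.

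**The case against.** The other side has a good case on impact.

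- **Look-back:** SAP 9 defines prior medication as anything started before first dose, with no date limit in that definition, and lists what the CRF holds. No table is shown to change. This stands. The 84 days may be left over from the 12-week period that a protocol amendment shortened to 4 weeks, but the point rests on the current texts alone.
- **Tail:** the last-visit extension covers any subject who attends the 90-day visit. Later quarterly contacts collect survival, subsequent MDS therapy and AML progression only, so subjects without that visit may have little late medication data to lose. Drugs started before the cut-off and continued are still counted. These points stand and limit the size. They do not explain why the medication window differs from the adverse-event window.
- **SAP 7.4:** the table's title and its opening words restrict it to MDS treatment, and SAP 9 already provides a separate prior-medication table. A careful programmer would probably ignore the clause. That lowers the risk but does not make the sentence correct.

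A reader might infer that steroids given on Days 29 to 90 after durvalumab vanish from the report. The documents do not support this: SAP 9 lists all concomitant medications documented on the CRF for the safety population. A reader might also take the medication table as the main record of how immune events were treated. Protocol 11.2.5 separately has investigators report, for each adverse event, whether treatment was given.

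**Conclusion.** The conflicts are real in the current texts, both between SAP and protocol and within the SAP, and the consequence is minor.

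- SAP 7.4, followed literally, labels non-MDS drugs as prior MDS treatment.
- SAP 9 lets the concomitant-medication frequency table stop before the 90-day adverse-event window. The shortfall is at most 62 days if durvalumab was the last IP dose, 42 days if the last 21-day CC-486 course was completed, and less or none if CC-486 continued alone. It arises only in combination subjects with no later visit.
- The 84-day look-back misdescribes coverage by 56 days and removes no recorded data.

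The ceiling of about 20 subjects assumes 16 in each Phase 2 monotherapy cohort. It bounds those who could have received durvalumab, not those affected; the latter must also lack a later visit and have a medication first recorded after the cut-off. The documents do not give that number. Only descriptive tables are involved. The response rate, the two-stage decision rule and the adverse-event counts do not depend on these rules.

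**What to change.** Three sentences of the SAP need editing.

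1. **SAP 7.4:** delete the clause that brings in medications for any indication, and tabulate only the prior-MDS-treatment CRF, with no date limit.
2. **SAP 9, both window sentences:** end at 28 days after the last CC-486 dose or 90 days after the last durvalumab dose, or at the last study visit if later, as in Protocol Section 9.
3. **SAP 9, analysis-window sentence:** set the look-back to 28 days for non-MDS medications, and keep MDS treatments without a date limit.

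The cost is a short SAP amendment and a matching change to the table programs. No data need to be collected or re-collected.

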10. EFFICACY ANALYSIS

All efficacy analyses will be performed on the ITT population. Supportive efficacy analyses will also be performed using the evaluable population.

10.1. Primary Efficacy Analysis

The primary assessment of efficacy will be the overall rate of response (defined as CR, PR, or mCR), and HI as determined using the modified IWG 2006 response criteria for MDS.

Hematologic response (CR, PR, mCR, and HI) will be determined by investigator assessment and responses will also be derived, summarized and analyzed separately. The percentage of these responses will be estimated separately, and the corresponding 95% confidence interval will also be provided. The percentage of subjects with other response outcomes of stable disease, failure, relapse after CR or PR, and disease progression will also be presented.

- ***Hematologic Response*** (including CR, PR, mCR, SD, Failure, Relapse after CR or PR, and Cytogenetic Response) is defined according to modified IWG 2006 criteria. Subjects will be classified according to their best response achieved during treatment for the response categories of CR, PR, mCR, SD, and failure. Only subjects who achieve CR or PR will be included in the Relapse after CR or PR category. Subjects will be evaluated for cytogenetic response regardless of their response status in other categories. Hematologic response will be presented descriptively using counts and percentages.
- ***Cytogenetic Response*** Subjects will be classified as having a complete or partial response based on the best response achieved during treatment. Responses will be presented descriptively using counts and percentages.
- The response rates at the end of Stage 2 and the associated 90% confidence interval will be estimated for each cohort which completes Stage 2. Similar estimates for Stage 1 will be provided for any cohort which does not continue to Stage 2.
- The response rates at the end of Stage 2 will be compared between cohorts of SD and PD subjects (if both cohorts finished Stage 2) using the relative risk ratio or other appropriate methods. Specifically, if relative risk method is used, the ratio of response rates for both cohorts and the associated 90% confidence interval will be estimated.

10.2. Secondary Efficacy Analyses

10.2.1. Overall Survival

- Overall survival (OS), time to death from any cause, will be calculated using date of first dose and date of death, or date of last follow-up for censored subjects. Time to death from any cause is defined as the time between first dose and death from any cause.
- All subjects will be followed until drop-out, death, or study termination. Drop-out may be due to withdrawal of consent from further data collection or loss to follow-up. Subjects

who drop-out or are alive at study termination will have their OS times censored at the time of last contact, as appropriate.

- The OS will be estimated using Kaplan-Meier (KM) method.

